7.5.1. Blinding

Study patients, the principal investigators, and study site personnel will remain blinded to all randomization assignments throughout the study. The blinded Regeneron Medical/Study Director, Study Monitor, and any other Regeneron and contract research organization (CRO) personnel who are in regular contact with the study site will remain blinded to all patient randomization assignments.

All study personnel will be blinded to data during each study part until the respective database lock. Part A will be unblinded while Part B is ongoing.

Blinded study drug kits coded with a medication numbering system will be used. In order to maintain the blind, lists linking these codes with product lot numbers will not be accessible to individuals involved in study conduct.

Anti-drug antibody, drug concentration results, and any post-treatment tissue eosinophil counts and histologic results, and biomarker results (eotaxin-3, thymus and activation-regulated chemokine [TARC], total IgE and allergen-specific IgEs) will not be communicated to the sites, and the sponsor's blinded operational team will not have access to results associated with patient identification until after the database is locked for the respective study part.

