5.1.3. Part C (28-Week Extended Active Treatment Period)

At the end of the double-blind treatment visit (week 24), eligible patients in Parts A and B may enter an approximately 28-week extended active treatment period where all patients will receive active treatment with dupilumab but only patients in Part B will be blinded to treatment regimen in Part C. The eligibility criteria for Part C are provided in Section 6.2.3.

Patients from Part A who are randomized to placebo during the double-blind treatment period will receive dupilumab 300 mg QW during Part C. Patients from Part A who are randomized to dupilumab 300 mg QW during the double-blind treatment period will continue to receive dupilumab 300 mg QW during Part C.

Patients from Part B who are randomized to placebo during the double-blind treatment period will be re-randomized in a 1:1 ratio to dupilumab 300 mg QW or dupilumab 300 mg Q2W. Patients randomized to dupilumab 300 mg Q2W will also receive matching placebo alternating with dupilumab doses so the injection frequency will be identical for both groups for regimen-blinding purposes. All other patients will remain on the same dupilumab dose regimen to which they are randomized during the double-blind treatment period. Treatment assignment in Part C will be managed by an interactive voice/web response system (IVRS/IWRS) to maintain blinding of treatment assignment in Part B.

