10.4.9. Timing of Statistical Analysis

Multiple steps of analyses are planned for this study.

- The first database lock will occur after the last Part A patient has completed their end of Part A visit including patients who have terminated early in Part A.
- The second database lock will occur after the last Part A patient has completed their week 52 visit of Part C including Part A patients who have terminated early in Part A or Part C.
- The third database lock will occur after the last Part B patient has completed their end of Part B visit including patients who have terminated early in Part B.
- After the last patient completes the last visit in Part C, analysis of all week 52 efficacy and safety endpoints may be performed.

- The last database lock will occur after the last patient completes their last end of study visit. The end-of-study analysis will include data through the end of the 12-week follow-up period.

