- Major elective surgical procedures
- Esophageal dilation (may be used as rescue procedure)
- Initiation or change of food-elimination diet regimen

Patients may receive the prohibited medications/procedures listed above as needed during the follow-up period, with the exception of live (attenuated) vaccine, which should not be used within 3 months after the last dose of study drug. Investigators are advised to prescribe prohibited medications/procedures judiciously, only when they are absolutely required for the appropriate management of study patients.

Blinded adjudication of prohibited medications and procedures will be performed by the medical monitor before database locks with documented procedures.

Rescue treatments (including both medications and procedures): If medically necessary (eg, for treatment of intolerable EoE symptoms), rescue medications (systemic and/or swallowed topical corticosteroids) or emergency esophageal dilation are allowed for study patients in Part B and C. If possible, an endoscopy with biopsy will be performed prior to the initiation of rescue therapy. Patients who undergo an endoscopy with biopsy due to the initiation of rescue therapy will not undergo the scheduled end of treatment visit endoscopy/biopsy at weeks 24 and 52. Patients who receive rescue treatment in Part B will not be eligible for the Part C extended active treatment period unless an endoscopy with biopsy is performed prior to the initiation of rescue treatment. However, if the endoscopy with biopsies cannot occur due to COVID-19 restrictions, rescue treatment should not be delayed, and these patients will be eligible for Part C. Patients receiving rescue therapy may continue to receive study drug. They will remain blinded and will be asked to return to the clinic for all remaining study visits and participate in all assessments for these visits except for endoscopy/biopsy, as noted above.

Blinded adjudication of rescue treatments will be implemented before database locks by considering the type of medication or procedure, indication, timing, frequency and the potential

impact of the use of the medication or procedure. The rescue treatments will be adjudicated by the medical director (or medical monitor) with documented procedures.

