## **8. TIMING OF STATISTICAL ANALYSIS**

Primary analysis and final analysis are planned for Part B patients. The primary analysis will be performed when the last Part B patient has completed their end of Part B visit including patients who have terminated early in Part B. The assessments of primary, secondary, and exploratory efficacy endpoints through the end of Part B during the primary analysis will be the final (and only) analyses of these endpoints. Hence, there will be no need for alpha adjustment due to this primary analysis. Available Part B patients' Part C data will also be analyzed and evaluated, including assessment of secondary endpoints at week 52 for patients for whom this is evaluable at time last patient completes end of Part B. The final analysis for Part B patients will occur when all patients who entered the 12-week follow-up period immediately from Part B or Part C completed the follow-up period. The Part B CSR will be written separately from Part B patients' Part C CSR.

To maintain study integrity with respect to the post Part B visits and analyses, a dissemination plan will be written. This plan will clearly identify the team (including the statistician) that will perform the Part B analysis and all related activities, restrict other clinical team members and other Sponsor personnel from access to individual patient treatment allocation and site level analysis results, and ensure that the dedicated team will not participate in the data review or data decisions for the following post treatment analyses. However, the dedicated team can participate in the analysis following the final database lock.

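### Protocol 7.5.1 lets the sponsor's blinded operational team see patient-identified drug concentration, ADA, histology and biomarker results from the Part B lock, while some of those patients may still be in regimen-blinded Part C

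*Protocol*

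**What the plan says.** Protocol 7.5.1 keeps patients, investigators and site staff blinded to assignments for the whole study. Sponsor and CRO staff "who are in regular contact with the study site will remain blinded to all patient randomization assignments", and no end date is given. For data, the rule runs by study part: "All study personnel will be blinded to data during each study part until the respective database lock". The last paragraph of 7.5.1 treats ADA, drug concentration, post-treatment tissue eosinophil and histology results, and biomarkers separately. They are not sent to sites, and for the sponsor's blinded operational team the rule is that it "will not have access to results associated with patient identification until after the database is locked for the respective study part".

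On timing, Protocol 10.4.9 states: "The third database lock will occur after the last Part B patient has completed their end of Part B visit". On Part C, Protocol 5.1.3 says that "only patients in Part B will be blinded to treatment regimen in Part C". Placebo patients from Part B are re-randomized 1:1 to QW or Q2W, and for the rest: "All other patients will remain on the same dupilumab dose regimen to which they are randomized during the double-blind treatment period".

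SAP section 8 adds a safeguard for the period after the Part B analysis. A dissemination plan is to name the team that performs that analysis, to "restrict other clinical team members and other Sponsor personnel from access to individual patient treatment allocation and site level analysis results", and to keep the dedicated team out of later data review and data decisions until the final lock.

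**The concern.** The assignment blind for site-facing sponsor staff is open-ended, but the embargo on results that may hint at assignment ends at the Part B lock. By giving these results their own embargo, the protocol itself treats them as potentially unblinding. The SAP section 8 list names allocation and site-level results; it does not name patient-level drug concentration, ADA, histology or biomarkers.

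The regimen blind in Part C was deliberate. The Amendment 2 entry in the amendment history records that Part C was changed from open-label, at a health authority's request, and that alternating placebo injections were added to mask the regimen for Part B patients.

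Sponsor-side judgement continues during Part C. SAP 4.3 requires blinded adjudication of prohibited medication by the medical monitor before database locks, and on rescue it says: "The rescue treatments will be adjudicated by the medical director (or medical monitor) with documented procedures". SAP 11.4 gives the medical monitor manual adjudication of some AESI terms before lock. If staff who make these decisions, or who deal with sites, could infer the regimen, rescue counts and AESI summaries by regimen in Part C could be affected.

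**Working it through.** The plan gives no figure to reproduce on this point. The check sets the timeline against the access rule, then asks whom it could touch and which results could reveal what.

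**1. Timeline.** The Part B lock follows the last Part B patient's week 24 visit (Protocol 10.4.9). Part C runs 28 weeks from week 24 (Protocol 5.1.3). A patient who enters Part C at the end of Part B accrual therefore has up to 28 weeks of regimen-blinded treatment left, less the time taken to lock.

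**2. Patients whose Part B regimen is also their Part C regimen.** Three arms of 70 are planned (Protocol 10.2). The two active arms carry over: 2 × 70 = 140, and 140/210 = 67%. The other 70 (33%) are re-randomized, so their Part B results cannot show their Part C regimen.

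**3. How many are still in Part C at the lock.** Accrual length and lock lag are not in the documents. Assume uniform accrual, full entry into Part C and no dropout. The share is (28 − lag in weeks)/(accrual in weeks), capped at 1, and is multiplied by 140.

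| Accrual (weeks) | No lag: share, patients | 8-week lag: share, patients |
|---|---|---|
| 28 | 100%, 140 | 71%, 100 |
| 52 | 54%, 75 | 38%, 54 |
| 78 | 36%, 50 | 26%, 36 |
| 104 | 27%, 38 | 19%, 27 |

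The range is about 27 to 140. If the 15% dropout assumed for sample size (SAP 2.3) were applied to the upper bound, it would be 140 × 0.85 = 119.

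**4. What histology could reveal.** The planning response rates are 5.1% on placebo and 59.5% on each dupilumab arm, with equal effects assumed for QW and Q2W (Protocol 10.2). With 1:1:1 allocation:
- P(active given responder) = 2 × 0.595/(2 × 0.595 + 0.051) = 1.190/1.241 = 96%.
- P(QW given active responder) = 0.595/(0.595 + 0.595) = 50%.

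Histology thus points to active versus placebo in Part B. Under the plan's own assumption it says nothing about QW versus Q2W, which is the only thing blinded in Part C.

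**5. What drug concentration could reveal.** Samples are taken at baseline and weeks 12 and 24 (Protocol Table 1). Placebo patients receive no dupilumab, and QW patients receive twice as many 300 mg doses as Q2W patients over the same period. Concentration is therefore the plausible route to the regimen. The documents give no values by regimen. Sampling is sparse (Protocol 4.3), and body weight is named as the main covariate for exposure (Protocol 3.2.2). The degree of separation cannot be computed, and no ADA or biomarker difference by regimen is given either.

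**The case against.** The strongest reply is that 7.5.1 only says how long a bar lasts. Nothing orders or schedules a release, and the same section keeps site-facing sponsor staff blinded to assignments without limit. Read together, that standing duty should stop any release that would reveal an assignment. SAP section 8 also plans a control for exactly this period. The dissemination plan is a separate document, and one SAP sentence that does not list drug concentration is no proof that the plan omits it. This stands in part: access is permitted rather than given, and the plan may already cover it. But the only explicit rule on these results still ends at the Part B lock, and nothing in the two documents extends it.

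The second reply is that little depends on it, and most of this stands:
- Part C has no formal hypothesis testing (SAP 5.6.2), and the formal Part B tests compare each regimen with placebo (SAP 5.6.3).
- Part C efficacy uses all observed values whether or not rescue was used (SAP 5.6.2), so rescue adjudication cannot change week 52 efficacy values.
- Histology is read by blinded central pathologists, and the DSQ is a patient diary.

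A reader might go further and infer that the Part C blind is broken, that drug concentration identifies the regimen of 140 patients, or that the week 52 efficacy comparison is compromised. The documents do not support these readings. They show a permitted route, not a disclosure. They contain no concentrations by regimen. The figure of 140 is a ceiling that needs full entry into Part C and every carry-over patient still there at the lock.

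**Conclusion.** The point holds as a gap in the access rule. From the Part B lock, 7.5.1 permits the operational team to see patient-identified results that may bear on a regimen still being given under blind. This works against the open-ended assignment blind in the same section.

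Its reach is limited to patients from the active arms who are still in Part C at the lock: at most about 140 of 210, and about 27 to 140 under the accrual and lag assumptions above. Patients and sites remain blinded to assignments, and the Part B co-primary tests and alpha are untouched. What remains exposed is sponsor-side review of AESI terms, rescue and prohibited medication, and contact with sites during Part C.

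The size of any bias cannot be computed. The conclusion assumes that the operational team, whose membership is not defined, includes or informs the people who make those decisions, and that concentration carries some information on QW versus Q2W. It is worth correcting because the change is cheap, not because any loss of blinding has been shown.

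**What to change.** In Protocol 7.5.1, for Part B patients who enter Part C, withhold patient-identified drug concentration, ADA, histology and biomarker results from the blinded operational team until the lock that covers those patients' Part C data. State that this does not limit access by the DMC (Protocol 5.3.1), by pharmacovigilance for regulatory reporting (Protocol 7.5.3) or by the dedicated Part B analysis team (SAP section 8). Add the same results to the restricted items in the SAP section 8 dissemination plan.

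Protocol 10.4.9 names no separate lock for the Part C data of Part B patients before the last database lock. The amended sentence should therefore say which lock is meant.

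The cost is one sentence in the protocol and one in the dissemination plan, with no new procedure or staff. The downside is that the operational team waits longer for patient-level laboratory results.

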7.5.2. Emergency Unblinding

Unblinding of treatment assignment for a patient may be necessary due to a medical emergency or any other significant medical event (eg, pregnancy).

- If unblinding is required:
 - Only the investigator will make the decision to unblind the treatment assignment.
 - Only the affected patients will be unblinded.
 - The designated study pharmacist(s)/designee at the study site will provide the treatment assignment to the investigator. If there is no study pharmacist, the investigator for the site will unblind the patient.
 - The investigator will notify Regeneron and/or designee as soon as possible after unblinding the patient.

Treatment assignment is not to be provided to site personnel, other than the unblinded study pharmacist (when applicable), at any time during the conduct of the study, except in the case of a true emergency. In the event that there is no study pharmacist, the individual at the site fulfilling that role will be the only unblinded member of the site personnel.

7.5.3. Unblinding for Regulatory Reporting Purposes

Treatment assignments for certain patients may be unblinded to Pharmacovigilance personnel for the purpose of regulatory reporting of suspected unexpected serious adverse reactions (SUSARs) to health authorities in accordance with local regulations.

7.6. Treatment Logistics and Accountability

7.6.1. Packaging, Labeling, and Storage

A medication numbering system will be used to label blinded investigational study drug. Lists linking medication numbers with product lot numbers will be maintained by the groups (or companies) responsible for study drug packaging. In order to maintain the blind, these lists will not be accessible to individuals involved in study conduct.

Study drug will be stored at the site at a temperature of 2°C to 8°C; storage instructions will be provided in the pharmacy manual.

7.6.2. Supply and Disposition of Treatments

Study drug will be shipped at a temperature of 2°C to 8°C to the investigator or designee at regular intervals or as needed during the study. At specified time points during the study (eg, interim site monitoring visits), at the site close-out visit, and following drug reconciliation and documentation by the site monitor, all opened and unopened study drug will be returned to the sponsor or designee for destruction, unless it's specified that the site may perform their own destruction.

7.6.3. Treatment Accountability

All drug accountability records must be kept current.

The investigator must be able to account for all opened and unopened study drug. These records should contain the dates, quantity, and study drug that is:

- dispensed to each patient,
- returned from each patient (if applicable), or
- disposed of at the site or returned to the sponsor or designee.

All accountability records must be made available for inspection by the sponsor and regulatory agency inspectors; photocopies must be provided to the sponsor at the conclusion of the study.

7.6.4. Treatment Compliance

All drug compliance records must be kept current and made available for inspection by the sponsor and regulatory agency inspectors.

7.7. Concomitant Medications and Procedures

Any treatment administered from the time of informed consent to the final study visit will be recorded. Any treatment administered from the time of first dose of study drug to the final study visit will be considered concomitant medication; this includes medications that were started before the study and are ongoing during the study.

7.7.1. Prohibited Medications and Procedures

Treatment with the following concomitant medications is prohibited through week 52:

- Swallowed topical corticosteroids (may be used as rescue treatment for EoE)
- Systemic corticosteroids (may be used as rescue treatment for EoE)
 - Note: One-time use of a corticosteroid as a part of the anesthetic preparation used during each endoscopy procedure is allowed.
- Systemic immunosuppressive/immunomodulating drugs (including, but not limited to, omalizumab, cyclosporine, mycophenolate-mofetil, azathioprine, methotrexate, IFN- γ , or other biologics)
- Treatment with an investigational drug (other than dupilumab)
- Initiation, discontinuation, or change in dosage regimen of the following medications within 8 weeks prior to the baseline endoscopy (stable doses of these medications are allowed)
 - Proton pump inhibitors, unless used for a required PPI trial during the screening period or in patients who present at the initial screening visit with current use of PPIs
 - Systemic leukotriene inhibitors

- Nasal and/or inhaled corticosteroids
- Initiation of SCIT, or change in dose for those patients on a stable dose of SCIT within 1 year prior to screening
- SLIT
- OIT
- Treatment with an investigational drug (other than dupilumab)
- Treatment with a live (attenuated) vaccine

Chickenpox (varicella)	Oral typhoid
FluMist-Influenza	Rubella
Intranasal influenza	Smallpox (vaccinia)
Measles (rubeola)	Yellow fever
Measles-mumps-rubella combination	Bacille Calmette-Guerin
Measles-mumps-rubella-varicella combination	Rotavirus
Mumps	Varicella zoster (shingles)
Oral polio (Sabin)	

The following concomitant procedures are prohibited during study treatment (through week 52):

- Major elective surgical procedures
- Esophageal dilation (may be used as rescue procedure)
- Initiation or change of food-elimination diet regimen

7.7.2. Permitted Medications and Procedures

Other than the prohibited medications listed in Section 7.7.1, treatment with concomitant medications are permitted during the study. Medications used to treat chronic disease such as diabetes and hypertension are also permitted. If there is any question regarding whether a concomitant medication may be used during the study, the study site should contact the medical monitor.

7.7.3. Restricted Medications and Procedures during the Follow-Up Period

Patients may receive the prohibited medications/procedures listed in Section 7.7.1 as needed during the follow-up period, with the exception of live (attenuated) vaccine, which should not be used within 3 months after the last dose of study drug. Investigators are advised to prescribe prohibited medications/procedures judiciously, only when they are absolutely required for the appropriate management of study patients.

8. STUDY SCHEDULE OF EVENTS AND PROCEDURES

8.1. Schedule of Events

Study assessments and procedures are presented by study period and visit in [Table 1](#) for the screening period and double-blind treatment period in Parts A and B, in [Table 2](#) for the extended active treatment period in Part C, and in [Table 3](#) for the follow-up period, ET visit, and unscheduled visit.

In light of the public health emergency related to COVID-19, the continuity of clinical study conduct and oversight may require implementation of temporary or alternative mechanisms. Examples of such mechanisms may include, but are not limited to, any of the following: phone contact, virtual visits, telemedicine visits, online meetings, non-invasive remote monitoring devices, use of local clinic or laboratory locations, and home visits by skilled staff. Additionally, no waivers to deviate from protocol enrollment criteria due to COVID-19 will be granted. All temporary mechanisms utilized, and deviations from planned study procedures are to be documented as being related to COVID-19 and will remain in effect only for the duration of the public health emergency.

Table 1: Parts A and B Schedule of Events – Screening Period and Double-Blind Treatment Period

Study Procedure	Screening Period		24-Week Double-Blind Treatment Period ¹⁸								
	Screening ¹ V1	Screening Endoscopy/ Biopsy ² V2	Baseline V3	V4	V5	V6	V7	V8	V9	V10	DB EOT V11 ³
Week (W)				W1	W2	W4	W8	W12	W16	W20	W24 ³
Day (D)	D-85 to D-29 ¹	D-21 ²	D1	D8	D15	D29	D57	D85	D113	D141	D169
Visit Window (Days [d])		±7 d		±3 d	±3 d	±3 d	±3 d	±3 d	±3 d	±3 d	+7 d
Screening⁴/Baseline:											
Informed consent and assent	X										
Inclusion/Exclusion criteria	X	X	X								
Med. history, Demographics	X										
Randomization ^{2a}			X ^{2a}								
Treatment:											
Training for self-injection ⁵			X	X ^{6a}	X ^{6a}						
Administer study drug ^{6, 6a}			X	X	X	X	X	X	X	X	
Study drug dispensation ^{6, 6a}				X	X	X	X	X	X	X	
Study drug accountability				X ^{6a}	X ^{6a}	X	X	X	X	X	X
Concomitant medications/procedures	X	X	X	X	X	X	X	X	X	X	X
Efficacy:⁷											
DSQ PRO (daily) ⁸	assessed by patient daily using eDiary										
PGIC ⁹								X		X	X
PGIS ⁹			X					X		X	X
EoE Impact Questionnaire ¹⁰			X					X			X
EoE Symptom Questionnaire ¹⁰			X					X			X
TNSS ¹¹			X					X			X
RQLQ(S)+I2 ¹¹			X					X			X
ACQ-5 ¹¹			X					X			X
POEM ¹¹			X					X			X
EQ-5D-3L	X ¹⁷		X ¹⁷								
EoE-EREFS ^{2,12}		X ^{2, 2a, 4}									X ^{2, 2b}
Endoscopy with biopsies (histology, IHC, RNA, EndoFLIP) ²		X ^{2, 2a, 4}									X ^{2, 2b}

Study Procedure	Screening Period		24-Week Double-Blind Treatment Period ¹⁸								
	Screening ¹ V1	Screening Endoscopy/ Biopsy ² V2	Baseline V3	V4	V5	V6	V7	V8	V9	V10	DB EOT V11 ³
Week (W)				W1	W2	W4	W8	W12	W16	W20	W24 ³
Day (D)	D-85 to D-29 ¹	D-21 ²	D1	D8	D15	D29	D57	D85	D113	D141	D169
Visit Window (Days [d])		±7 d		±3 d	±3 d	±3 d	±3 d	±3 d	±3 d	±3 d	+7 d
Safety: ^{7, 7a, 18}											
Vital signs ¹³	X	X	X ¹³	X ^{13, 13a}	X ^{13, 13a}	X ^{13, 13a}	X ^{13a}	X ^{13a}	X ^{13a}	X ^{13a}	X
Physical examination	X										X
ECG	X										X
Height	X										X ¹⁴
Weight	X	X	X		X	X	X	X	X	X	X
Adverse events	X	X	X	x	X	X	X	X	X	X	X
Laboratory Testing: ^{7, 7a}											
Hematology, Chemistry	X		X					X			X
Serology tests ¹⁵	X										
Serum FSH	X										
Pregnancy test ¹⁶	Serum	Urine	Urine			Urine	Urine	Urine	Urine	Urine	Urine
Urinalysis	X		X					X			X
PK and ADA: ^{7, 7a}											
PK sample			X					X			X
ADA sample			X					X			X
Biomarkers and Genomics: ^{7, 7a}											
Whole blood DNA (optional)			X								
Whole blood RNA (optional)	X		X								X
Plasma Eotaxin-3	X		X			X		X			X
Serum TARC	X		X			X					X
Serum Total IgE	X		X			X		X			X
Allergen-specific IgE, IgG4	X		X			X		X			X
Future Biomarker Serum/Plasma	X		X			X		X			X

ADA = anti-drug antibody; DB EOT = end of double-blind treatment period; DSQ = Dysphagia Symptom Questionnaire; ECG = electrocardiogram; EoE-EREFS = Eosinophilic Esophagitis-Endoscopic Reference Score; EQ-5D-3L = European Quality of Life 5-dimension (version 3L; 3-level); IHC = immunohistochemistry; PGIC = Patient Global Impression of Change of Dysphagia; PGIS = Patient Global Impression of Severity of Dysphagia; POEM =

Patient-Oriented Eczema Measure; PRO = patient-reported outcome; PK = pharmacokinetic; RQLQ(S)+12 = Rhinoconjunctivitis Quality of Life Questionnaire for patients aged 12+ years; TNSS = Total Nasal Symptom Score; V = visit

Table 2: Part C Schedule of Events – Extended Active Treatment Period

	28-Week Extended Active Treatment Period ¹⁴								
Study Procedure	V11 ¹	V12	V13	V14	V15	V16	V17	V18	EOT V19
Week (W)	W24 ¹	W26	W28	W32	W36	W40	W44	W48	W52
Day (D)	D169	D183	D197	D225	D253	D281	D309	D337	D365
Visit Window (Days [d])	+7 d	±7 d	±7 d	±7 d	±7 d	±7 d	±7 d	±7 d	+7 d
Treatment:²									
Administer study drug ^{3, 4, 4a}	X	X	X	X	X	X	X	X	
Study drug dispensation ^{4, 4a}	X	X	X	X	X	X	X	X	
Study drug accountability		X	X	X	X	X	X	X	X
Concomitant medications/procedures		X	X	X	X	X	X	X	X
Efficacy:²									
DSQ eDiary ⁵	←----- completed daily by patient -----→								
PGIC ⁶					X				X
PGIS ⁶					X				X
EoE Impact Questionnaire ⁷					X				X
EoE Symptom Questionnaire ⁷					X				X
TNSS ⁸					X				X
RQLQ(S)+12 ⁸					X				X
POEM ⁸					X				X
ACQ-5 ⁸					X				X
EoE-EREFS ^{9, 10}									X ^{10, 10a}
Endoscopy with biopsies (histology, IHC, RNA, EndoFLIP) ¹⁰									X ^{10, 10a}
Safety: ^{2, 2a, 14}									
Vital signs ¹¹	X ¹¹	X ¹¹	X	X	X	X	X	X	X
Height ¹²									X
Weight		X	X	X	X				X
Physical examination									X
ECG									X
Adverse events		X	X	X	X	X	X	X	X

	28-Week Extended Active Treatment Period ¹⁴								
Study Procedure	V11 ¹	V12	V13	V14	V15	V16	V17	V18	EOT V19
Week (W)	W24 ¹	W26	W28	W32	W36	W40	W44	W48	W52
Day (D)	D169	D183	D197	D225	D253	D281	D309	D337	D365
Visit Window (Days [d])	+7 d	±7 d	±7 d	±7 d	±7 d	±7 d	±7 d	±7 d	+7 d
Laboratory Testing: ^{2, 2a}									
Hematology, Chemistry					X				X
Pregnancy test ¹³		Urine		Urine	Urine	Urine	Urine	Urine	Urine
Urinalysis					X				X
PK and ADA: ^{2, 2a}									
PK Sample				X					X
ADA sample				X					X
Biomarkers: ^{2, 2a}									
Whole blood RNA (optional)									X
Plasma Eotaxin-3		X		X					X
Serum TARC									X
Serum Total IgE		X		X					X
Allergen-specific IgE, IgG4		X		X					X
Future Biomarker Serum/Plasma		X		X					X

ADA = anti-drug antibody; DSQ = Dysphagia Symptom Questionnaire; ECG = electrocardiogram; EoE-EREFS = Eosinophilic Esophagitis-Endoscopic Reference Score; EOT = end of extended active treatment period; IHC = immunohistochemistry; POEM = Patient-Oriented Eczema Measure; PRO = patient reported outcome; PGA = physician global assessment; PGIC = Patient Global Impression of Change of Dysphagia; PGIS = Patient Global Impression of Severity of Dysphagia; PK = pharmacokinetic; RQLQ(S)+12 = Rhinoconjunctivitis Quality of Life Questionnaire for patients aged 12+ years; TNSS = Total Nasal Symptom Score; V = visit

Table 3: Follow-up Period, Early Termination Visit, and Unscheduled Visit

Study Procedure	12-Week Follow-Up EOS Visit	Early Termination during 12-Week Follow-Up ¹	Early Termination during Parts A, B, or C ¹	Unscheduled Visit before Rescue Treatment	Unscheduled Visit for Other Reasons
Week (W)	12 weeks after EOT visit				
Day (D)	84 days after EOT visit				
Visit Window (Days [d])	±7 d				
Concomitant medications/procedures ¹⁰	X	X	X	X	X
Efficacy:					
DSQ eDiary ²	←completed daily by patient→		X	X	
PGIC ³			X	X	
PGIS ³			X	X	
EoE Impact Questionnaire ⁴			X	X	
EoE Symptom Questionnaire ⁴			X	X	
TNSS ⁵			X	X	
RQLQ(S)+I2 ⁵			X	X	
ACQ-5 ⁵			X	X	
POEM ⁵			X	X	
EoE-EREFS ^{6,7}			X ^{7, 7a}	X ⁸	
Endoscopy with biopsies (histology, IHC, RNA) ⁷			X ^{7, 7a}	X ⁸	
Safety¹⁰:					
Vital signs	X	X	X	X	
Height ⁹			X		
Weight	X	X	X		
Physical examination			X		
ECG			X		
Adverse events	X	X	X	X	X
Laboratory Testing¹⁰:					
Hematology, Chemistry	X	X	X		
Pregnancy test	Urine	Urine	Urine		
Urinalysis	X	X	X		

Study Procedure	12-Week Follow-Up EOS Visit	Early Termination during 12-Week Follow-Up ¹	Early Termination during Parts A, B, or C ¹	Unscheduled Visit before Rescue Treatment	Unscheduled Visit for Other Reasons
Week (W)	12 weeks after EOT visit				
Day (D)	84 days after EOT visit				
Visit Window (Days [d])	±7 d				
PK and ADA¹⁰:					
PK Sample	X	X	X	X	
ADA sample	X	X	X	X	X
Biomarkers:					
Future Biomarker Serum/Plasma (optional)			X		

ADA = anti-drug antibody; DSQ = Dysphagia Symptom Questionnaire; ECG = electrocardiogram; EoE-EREFS = Eosinophilic Esophagitis-Endoscopic Reference Score; EOS = end of study (visit); EOT = end of treatment period; POEM = Patient-Oriented Eczema Measure; PRO = patient-reported outcome; PGA = physician global assessment; PGIC = Patient Global Impression of Change of Dysphagia; PGIS = Patient Global Impression of Severity of Dysphagia; PK = pharmacokinetic; RQLQ(S)+12 = Rhinoconjunctivitis Quality of Life Questionnaire for patients aged 12+ years; TNSS = Total Nasal Symptom Score

